### **13.2 Sample Size and Power Calculations**

Subjects will enter this protocol from the AURORA 1 study in order to provide the opportunity of an additional 24 months of treatment (total of 36 months of treatment); no sample size calculation is required.

### **13.3 Populations**

#### **13.3.1 Intent-to-Treat Set**

The intent-to-treat (ITT) set will be based on ITT principles and will consist of all subjects who are consented to treatment. This group will be analyzed based on the treatment to which the subject was randomized in the AURORA 1 study.

#### **13.3.2 Safety Set**

The safety set will consist of all subjects who receive at least 1 dose of study drug in the continuation study. The subjects in this group will be analyzed based on the treatment they received. Subjects who receive treatment from more than 1 arm will be assigned to the Orelvo arm.

### **13.4 Background and Demographic Characteristics**

Demographic and clinical disease characteristics will be summarized by treatment arm in a descriptive manner but no statistical tests will be performed.

### **13.5 Study Treatment**

Compliance to the study treatment will be determined by dividing the number of softgel capsules taken by the expected number of softgel capsules to be taken (based on prescribed dose) over the subject's participation in the study.

Results will be summarized by means of descriptive statistics (n, mean, standard deviation, median, minimum, and maximum) and frequency tables, by treatment arm.

## 13.6 Concomitant Therapy

All concomitant medications will be coded by the WHO Anatomical Therapeutic Chemical Drug Reference List classification. The version used will be provided in the clinical study report.

## 13.7 Endpoint Evaluations

### 13.7.1 Primary Safety Endpoint

The primary safety endpoint is as follows:

- AE profile and routine biochemical and hematological assessments

### 13.7.2 Secondary Efficacy Endpoints

#### 13.7.2.1 Key Secondary Efficacy Endpoints

- Proportion of subjects in renal response at Months 12, 18, 24, 30, and 36 defined as:
  - UPCR of  $\leq 0.5$  mg/mg
  - eGFR  $\geq 60$  mL/min/1.73 m^2 or no confirmed decrease from baseline in eGFR of  $>20\%$
  - Received no rescue medication for LN (see Section 7.8, [Prohibited Therapy and Concomitant Treatment](#))
  - Did not receive more than 10 mg prednisone for  $\geq 3$  consecutive days or for  $\geq 7$  days in total during the 8 weeks prior to the renal response assessment
- Subjects who withdraw from the study prior to the response assessment will be defined as non-responders.
- Proportion of subjects in partial renal response at Months 12, 18, 24, 30, and 36 defined as a 50% reduction from baseline in UPCR.
- Renal flare as adjudicated by the CEC.
- Extra-renal flare as adjudicated by the CEC.
- SELENA-SLEDAI scores by visit.
- Change in UPCR, eGFR, urine protein, and serum creatinine from AURORA 1 baseline.

### 13.7.2.2 Other Secondary Efficacy Endpoints

- Change in immunology parameters (C3, C4, and anti-dsDNA) from AURORA 1 baseline.
- Change in HRQoL (SF-36) from AURORA 1 baseline.
- HRU.

### 13.7.2.3 [REDACTED]

## 13.8 Statistical and Analytical Methods

### 13.8.1 Safety Analysis

The primary safety endpoints are the AE profile and routine biochemical and hematological assessments at Month 36 (Section 13.7.1, [Primary Safety Endpoint](#)).

### 13.8.2 Efficacy Analysis

All the secondary efficacy analyses will be performed on the ITT set. Data for each visit (as well as change from AURORA 1 study baseline as required) will be summarized by treatment group and visit for each secondary endpoint.

#### 13.8.2.1 Response Endpoints

The following key secondary efficacy endpoints will be analyzed using the ITT population using logistic regression with terms for treatment group, baseline UPCR, biopsy class, and MMF use at baseline (from AURORA 1) in the model.

- Proportion of subjects in renal response at Months 12, 18, 24, 30, and 36.
- Proportion of subjects in partial renal response at Months 12, 18, 24, 30, and 36.

The results will be expressed as an odds ratio (and associated two-sided 95% CI) for Orelvo compared to placebo. Odds ratios greater than unity show the odds of response are greater for Orelvo than for placebo and therefore indicate a benefit of the Orelvo treatment arm.

### **13.8.2.2 Renal flare and Extra-renal flare**

The proportion of subjects with renal and extra-renal flares (as adjudicated by the CEC) will be analyzed in a similar fashion to the proportion of subjects achieving response.

### **13.8.2.3 Change from Baseline Endpoints**

The following secondary endpoints will be analyzed using a Mixed Effect Model Repeated Measures (MMRM). The MMRM model will include terms for treatment, visit, treatment by visit interaction, and baseline. Results will be expressed as differences between treatment arms (along with the associated 95% CI).

- Change in UPCR, eGFR, urine protein, and serum creatinine from AURORA 1 baseline at each visit.
- Change in immunology parameters (C3, C4, and anti-dsDNA) from AURORA 1 baseline at each visit.
- Change in HRQoL (SF-36) from AURORA 1 baseline at Months 12, 18, 24, 30, and 36.
- Change in SELENA-SLEDAI scores by visit at Months 12, 18, 24, and 36.

### **13.8.2.4 Healthcare Resource Utilization (HRU)**

- Healthcare Resource Utilization at Months 12, 15, 18, 21, 24, 27, 30, 33, and 36. Key aspects will be summarized by visit and changes over time will be explored.

## **13.9 Safety Evaluations**

Specific safety endpoints are as follows:

- Biochemical (including liver function tests) and hematological laboratory tests
- AE profile and routine biochemical and hematological safety parameters
- Vital signs (BP, HR, temperature) at specific time points and change from baseline
- Standard 12-lead ECGs change from baseline
- Discontinuations from treatment
- Concomitant medications

Laboratory values, vital signs, and other safety parameters providing numeric data will be summarized by visit as absolute values and change from baseline. Laboratory values outside of defined normal ranges will be summarized.

Adverse events will be coded using the latest available version of the Medical Dictionary for Regulatory Activities, the version of which will be provided in the clinical study report.

Treatment-emergent adverse events will be summarized by treatment arm, system organ class, and preferred term. SAEs, SAEs that led to death, and SAEs/AEs that led to withdrawal will also be summarized and listed.

Only AEs which started on or after the date of first dose of study treatment in AURORA 2 will be considered TEAEs, though all AEs after informed consent will be recorded. SAEs occurring at any time after informed consent will be summarized. All concomitant medications will be summarized.

Details of these and other analyses will be provided in the SAP.

All study data analyses involving laboratory values will be based on results from the central laboratory.

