### **10.2 Adverse Event Descriptors**

#### **10.2.1 Intensity/Severity Categorization**

The term "severe" is often used to describe the intensity (severity) of a specific event (as in mild, moderate, or severe myocardial infarction); however, the event itself may be of relatively minor medical significance (such as severe headache). This is not the same as "serious," which is based on subject/event outcome or action criteria usually associated with events that pose a threat to a subject's life or functioning. Seriousness (not severity) serves as a guide for defining regulatory reporting obligations.

In general, the intensity of a particular AE to be recorded is the worst intensity experienced by the subject during the course of the event. The medical assessment of intensity will be determined by using the following definitions:

- Mild: The AE is easily tolerated and does not interfere with usual activity.
- Moderate: The AE interferes with daily activity, but the subject is still able to function.
- Severe: The AE is incapacitating and the subject is unable to work or complete usual activity.

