3.1 Primary Endpoint

Adverse event (AE) profile and routine biochemical and hematological assessments. Estimand for AEs is the proportion of subjects reporting AEs in the Safety Population when comparing voclosporin and placebo at each visit. Estimands for biochemical and hematological assessments are the mean absolute values and mean changes from AURORA 1 baseline in the Safety Population when comparing voclosporin and placebo at each visit.

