6.11.7 Other Secondary Endpoints

Not applicable.

QMD Ref: [REDACTED]	Effective: 12Aug2019	Governing QMD: [REDACTED]
Confidentiality Statement		
This document is the property of [REDACTED] and may not be duplicated, copied, altered or removed from company without prior approval from [REDACTED] or in compliance with [REDACTED].		
REF: [REDACTED]		Page 27 of 37

		Controlled Quality Management Document	
		Sponsor:	Aurinia Pharmaceuticals
		Protocol Number:	AUR-VCS-2016-02
STATISTICAL ANALYSIS PLAN. PHASE 2-3-4			

A treatment-related TEAE is defined as a TEAE that is assessed by the Investigator or Sponsor as being related to study drug. If a TEAE has a missing relationship to study drug it is assumed to be related to the study drug for analysis purposes.

A disease-related TEAE is defined as a TEAE that is assessed by the Investigator or Sponsor as being related to the disease under study. If a TEAE has a missing relationship to the disease under study it is assumed to be related to the disease under study for analysis purposes.

Missing severity assessments will be summarised as severe.

Adverse event tables will comprise tables summarizing AURORA 2 TEAEs as well as some tables summarizing all TEAEs from month 0 to month 36.

The following tables will be presented for AURORA 2 TEAEs:

- Summary table of overall incidence, the number of events, relative risk and 95% CI (voclosporin:placebo) including the following top line summaries:
 - Any AE
 - Any TEAE
 - Any Treatment-Related TEAE
 - Any Serious TEAE
 - Any Treatment-Related Serious TEAE
 - Any TEAE Leading to Voclosporin/Placebo Modification
 - Any TEAE Leading to Voclosporin/Placebo Discontinuation
 - Any TEAE Resulting to Death
 - Disease-Related TEAE
 - Disease-Related Serious TEAE
- TEAEs by System Organ Class and Preferred term
- TEAEs by System Organ Class, Preferred term and severity
- Treatment-Related TEAE by System Organ Class and Preferred Term
- Treatment-Related TEAE by System Organ Class, Preferred Term and Severity
- TEAE by System Organ Class and Preferred Term Leading to Dose Modification
- TEAE by System Organ Class and Preferred Term Leading to Voclosporin/Placebo Discontinuation
- TEAE by System Organ Class and Preferred Term Resulting in Death
- Disease-Related TEAE by System Organ Class and Preferred Term
- Serious TEAE by System Organ Class and Preferred Term

QMD Ref: [REDACTED]	Effective: 12Aug2019	Governing QMD: [REDACTED]
Confidentiality Statement		

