This document is the property of [REDACTED] and may not be duplicated, copied, altered or removed from company without prior approval from [REDACTED] or in compliance with [REDACTED].		

REF: [REDACTED]

		Controlled Quality Management Document	
		Sponsor:	Aurinia Pharmaceuticals
		Protocol Number:	AUR-VCS-2016-02
STATISTICAL ANALYSIS PLAN. PHASE 2-3-4			

- Serious TEAE by System Organ Class, Preferred Term and Severity
- Treatment-Related, Serious TEAE by System Organ Class and Preferred Term
- Treatment-Related, Serious TEAE by System Organ Class, Preferred Term and Severity
- Serious TEAE by System Organ Class and Preferred Term Leading to Dose Modification
- Serious TEAE by System Organ Class and Preferred Term Leading to Voclosporin/Placebo Discontinuation
- Disease-Related, Serious TEAE by System Organ Class and Preferred Term

The following displays of AURORA 2 TEAEs will also be presented:

- Treatment-Emergent Adverse Events by Descending Frequency of Preferred Term
- Non-Serious Treatment-Emergent Adverse Events Occurring at an Incidence of >2% by Descending Frequency, System Organ Class and Preferred Term
- Treatment-Emergent Adverse Events by Descending Difference of Preferred Term between Treatment Group
- Listing of Serious TEAE
- Listing of TEAE Resulting in Death
- Listing of Post-Treatment Adverse Events Resulting in Death

The following displays will include all TEAEs from the start of AURORA 1:

- TEAE by System Organ Class and Preferred Term by Year of Onset
- Treatment-Related TEAE by System Organ Class, Preferred Term and Year of Onset
- TEAE by System Organ Class and Preferred Term Leading to Dose Modification by year of onset
- Serious TEAE by System Organ Class and Preferred Term by Year of Onset
- Treatment-Related, Serious TEAE by System Organ Class and Preferred Term and Year of onset
- Serious TEAE by System Organ Class and Preferred Term Leading to Dose Modification by year of onset

The following displays will be presented for all randomized subjects from Aurora 1?

- TEAE by System Organ Class and Preferred Term
- Serious TEAE by System Organ Class and Preferred Term

QMD Ref: [REDACTED]	Effective: 12Aug2019	Governing QMD: [REDACTED]
Confidentiality Statement		
This document is the property of [REDACTED] and may not be duplicated, copied, altered or removed from company without prior approval from [REDACTED] or in compliance with [REDACTED].		

REF: [REDACTED]

		Controlled Quality Management Document	

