		Sponsor:	Aurinia Pharmaceuticals
		Protocol Number:	AUR-VCS-2016-02
STATISTICAL ANALYSIS PLAN. PHASE 2-3-4			

In counting the number of AEs reported, a continuous event (i.e., reported more than once and which did not cease), will be counted only once for a subject; a non-continuous AE reported several times by the same subject will be counted as multiple events.

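### AURORA 2 TEAEs are defined by start date alone, so an AE that began in AURORA 1 and worsens later is missing from the AURORA 2 TEAE tables unless the site opens a new record

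*Protocol*

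**What the plan says.** Protocol 13.9 sets the rule: "Only AEs which started on or after the date of first dose of study treatment in AURORA 2 will be considered TEAEs". The same paragraph says that all AEs after consent are recorded and that "SAEs occurring at any time after informed consent will be summarized". It does not mention worsening of an ongoing event.

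Two further rules fix how a continuing event is handled. Under Protocol 10.2.1, "the intensity of a particular AE to be recorded is the worst intensity experienced by the subject during the course of the event". Under SAP 6.12.1, "a continuous event (i.e., reported more than once and which did not cease), will be counted only once for a subject".

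SAP 6.12.1 then lists two main groups of tables:

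- **AURORA 2 TEAEs.** A top-line table with relative risk and 95% CI, then tables by severity, by dose modification, by discontinuation and by death, among others.
- **The longer window.** The SAP promises "some tables summarizing all TEAEs from month 0 to month 36". The list introduced by "The following displays will include all TEAEs from the start of AURORA 1" has six displays: all TEAEs, treatment-related, leading to dose modification, serious, treatment-related serious, and serious leading to dose modification. All six are by year of onset. Two more displays, TEAEs and serious TEAEs by system organ class and preferred term, cover all subjects randomized in AURORA 1.

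SAP 3.1 words the primary estimand in terms of AEs: "Estimand for AEs is the proportion of subjects reporting AEs in the Safety Population when comparing voclosporin and placebo at each visit".

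The opening of SAP 6.12.1, where the SAP's own TEAE definition would be expected, is not in the text supplied.

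**The concern.** The primary objective is safety over the additional 24 months. A start-date rule suits a study whose subjects are untreated at entry. Here they have already had a year of randomized treatment (Protocol 5.2 and 6.1), so drug effects that begin early are already present at the AURORA 2 starting line.

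Take mild hypertension that starts in AURORA 1, is ongoing at Month 12, becomes severe at Month 20 and leads to study drug being stopped. The record keeps its AURORA 1 start date, so it is not an AURORA 2 TEAE. The subject cannot have a new onset of an event already under way, yet stays in the AURORA 2 denominator. If the arms differ in how many such events they bring in, or in how often these worsen, the AURORA 2 relative risk for that term reflects the difference in the wrong place or not at all.

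**Working it through.** The plan gives no rate, power or error figure for this comparison, so there is none to reproduce. The check has three parts.

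**1. Where the example event appears** (AURORA 1 onset, ongoing at entry, one record, severe and leading to discontinuation at Month 20)

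| Output | Does it show the event? |
|---|---|
| AURORA 2 TEAE rows of the relative-risk table (SAP 6.12.1) | No |
| AURORA 2 TEAEs by severity, dose modification, discontinuation (SAP 6.12.1) | No |
| Six displays from the start of AURORA 1 | Yes, but in its year of onset; no severity or discontinuation display is listed |
| Two displays for all AURORA 1 subjects | Counted by term; no severity, timing or discontinuation |
| Exposure-adjusted rates (SAP 6.12.1.1) | Counted; worsening not visible |
| SAE and withdrawal summaries (Protocol 13.9) | Promised if the event is serious or led to withdrawal; the SAP's listed discontinuation tables are for AURORA 2 TEAEs |
| Discontinuations by arm and visit (SAP 6.4); dose changes by visit interval (SAP 6.9) | Yes, without the AE term |
| Blood pressure by visit (SAP 6.12.3); laboratory shifts and eGFR slope (6.12.2); eGFR MMRM (6.11.2.4) | The measured value, not AE severity or action taken |

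The relative-risk table also has an *Any AE* row. The text does not say whether it includes AURORA 1-onset events.

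**2. Whether recording practice closes the gap**

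- Protocol 10.2.4 has worsening of disease symptoms or laboratory parameters recorded as an AE, marked either as worsening or by worst intensity. The second option leaves the original record in place.
- Protocol 10.2.5 says a further change in an abnormal laboratory value can be an AE. It covers laboratory values only.
- Hypertension as a drug effect falls under neither, so the same course may be one record at one site and two at another.
- Under SAP 6.2.6, an ongoing event with a missing start date is imputed to the first AURORA 2 dose and so counts. The same event with a known earlier date does not.

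**3. Size and direction, with assumed rates**

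Single chronic term: *o* = share with the event ongoing at entry, *r* = new-onset risk among the rest, *w* = probability that an ongoing event worsens.

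- Counted under the rule: (1 − o) × r. Including worsening: (1 − o) × r + o × w.
- Assume o = 20% voclosporin, 10% placebo; r = 10% in both; w equal in both.
- Counted: 0.80 × 0.10 = 8.0% vs 0.90 × 0.10 = 9.0%, RR 0.89.

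| w | Voclosporin: 0.08 + 0.20w | Placebo: 0.09 + 0.10w | RR |
|---|---|---|---|
| 5% | 9.0% | 9.5% | 0.95 |
| 10% | 10.0% | 10.0% | 1.00 |
| 15% | 11.0% | 10.5% | 1.05 |
| 25% | 13.0% | 11.5% | 1.13 |
| 35% | 15.0% | 12.5% | 1.20 |

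The break-even solves 0.08 + 0.20w = 0.09 + 0.10w, so w = 0.01/0.10 = 10%.

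Second model, in which new onset and worsening can both occur in one subject (apt for a group of terms): risk = 1 − (1 − r)(1 − o × w), with r = 10% vs 7%, so the onset-only RR is 1.43.

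| Case | o (voclosporin / placebo) | w (voclosporin / placebo) | Risk with worsening | RR |
|---|---|---|---|---|
| a | 10% / 10% | 20% / 20% | 11.8% / 8.9% | 1.33 |
| b | 20% / 10% | 20% / 20% | 13.6% / 8.9% | 1.54 |
| c | 20% / 10% | 10% / 30% | 11.8% / 9.8% | 1.21 |
| d | 10% / 20% | 20% / 20% | 11.8% / 10.7% | 1.10 |

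The onset-only rule understates the RR when the ratio of the added risks exceeds the onset-only RR. In (b) that ratio is 3.60/1.86 = 1.94, above 1.43. In (a), (c) and (d) it is below 1.43, and the rule makes voclosporin look worse.

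For any TEAE at 85% vs 80%, with 50% vs 40% ongoing and 20% worsening, the risks become 1 − 0.15 × 0.90 = 86.5% and 1 − 0.20 × 0.92 = 81.6%. The RR stays at 1.06. The effect lies in individual terms, not in overall incidence.

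**The case against.** The strongest reply is that much of the information appears elsewhere. A reader might infer from Protocol 13.9 that a worsening AURORA 1 event is never counted. The documents do not support that: part 1 of the working lists several outputs that include it or its consequences. Decreased GFR is especially well covered, by the recording provisions for laboratory worsening and by the eGFR analyses. Laboratory assessments are themselves part of the primary endpoint. This stands, and it limits the gap to the AURORA 2 TEAE tables. It does not close it, because none of these outputs is listed as a by-arm comparison, by term, of worsening or discontinuation that includes such events.

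A second reply is that the direction is assumed. This also stands. Protocol 1.2.5 reports more hypertension TEAEs on voclosporin in the earlier lupus nephritis trial, and discontinuation for decreased GFR in 1.1% on placebo against 7.9% and 5.7% on the two voclosporin doses. Protocol 1.2.4.2 reports an eGFR fall by Week 4. These make more ongoing events on voclosporin plausible. Against that, Protocol 1.2.5 says the proportion with an early eGFR drop then stayed stable and that mean blood pressure fell in all groups. Section 2.1 calls the renal and blood pressure risks reversible. Entry requires completing 52 weeks of treatment, which removes subjects who permanently stopped for such events.

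Third, the SAP may already contain a worsening clause in the part not supplied. SAP Section 9 lists no change to the protocol definition, but that proves little: it also omits region in the logistic model, the added AE-based eGFR response criterion and the move to several interim analyses.

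**Conclusion.** The point holds in a limited form. The protocol's rule is explicit. With one record at worst intensity and one count per continuous event, it leaves AURORA 1-onset events that worsen out of the AURORA 2 TEAE comparison unless a site opens a new record. The displays from the start of AURORA 1 place them in the year of onset and list no severity or discontinuation table. For a study whose primary objective is safety in those 24 months, that is an incompleteness worth correcting.

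A reader might also infer that the primary safety comparison is shown to be biased toward voclosporin. It is not. The documents give no arm-level rates of ongoing or worsening events, and the sign changes across the assumed cases. In the single-term illustration the rule understates the relative risk at every worsening probability shown, but the conclusion crosses 1 only above 10%. That result rests on twice as many ongoing events on voclosporin and equal onset and worsening risks. Bias toward voclosporin for early-onset chronic effects is plausible, not established. All of this is subject to the SAP's own TEAE definition.

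**What to change.** First check the opening of SAP 6.12.1. Then, in Protocol 13.9, and in SAP 6.12.1 if it does not already say so, define an AURORA 2 TEAE as an AE that either:

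- starts on or after the first AURORA 2 dose; or
- is ongoing at that dose and afterwards increases in severity, becomes serious, or leads to modification or discontinuation of study drug.

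Alongside this:

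- instruct sites to record the worsening with its own date, so that the same course is handled alike everywhere;
- in the by-year tables, assign a worsening to the year in which it occurs;
- add one table, by arm, of AEs ongoing at AURORA 2 entry, which would also show whether the arms differ in the way the illustration assumes.

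The cost is wording in two documents, an eCRF completion instruction, one extra table and minor programming. The downside is that AURORA 2 TEAE counts rise somewhat in both arms.
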